Participants will be given contact information to a dedicated staff if they have any questions of concerns regarding the study and their participation in the study. Additional psychological risk may occur as the study involves bringing up sensitive topics such as risky sexual behavior and personal data, to minimize this risk, participants will be ensured that their information is protected with the utmost care and that all their gathered information will only be used for researched purposes. Any adverse events will be recorded.

Statistics

Sample size calculation

The sample size was be calculated with the following components:

- α (two-tailed) of 0.05
- $\bullet \qquad \beta = 0.8$
- Obtained from a study with a peer-led safe sex online intervention for Hong Kong adolescents aged <25 (19)
 - o Standard deviation: 0.52
 - o Effect size: 0.21

Attrition rate: 15% in online studies (20, 21)

112 people per intervention arm

Data Analysis

Data will be analyzed using SPSS. Descriptive statistics will be carried out analyze the demographics of the target population. Differences in baseline demographic characteristics between the intervention and control group will be assessed using chi-squared tests.

For outcome evaluation, paired t-tests will be used to examine within group outcome changes. For the primary outcome that is a score, linear regression will be used to evaluate the difference between the control and intervention group.

Independent t-tests will be carried out to evaluate the score change within group and also between groups. The outcome difference at baseline and at follow-up will also be evaluated with linear regression.

Direct Access to Source Data/Documents

The investigator/institution will permit trial-related monitoring, audits, IRB/IEC review, regulatory inspections, providing direct access to source data/documents.

Quality Control and Quality Assurance

Ethics

Major ethical issues involve asking about sensitive information regarding risky sex behaviors, users' privacy, and legal issues. Participants will be ensured by the project's researchers that their information is kept strictly confidential. Researchers will also ensure that participants understand the purpose and procedure of every step of the project and participants will be provided with a contact for whenever they have any questions or concerns. Patients also understand that they are allowed to withdraw at any given point of the study.

Data Handling and Record Keeping

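### The protocol's β of 0.8 cannot produce 112 per arm; the figure needs power 0.80 and a raw difference of 0.21, and its attrition allowance falls 2 to 3 completers per arm short

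*Protocol*

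**What the plan says.** The Protocol (Statistics, Sample size calculation) gives a short list of inputs: α of 0.05, two-tailed; β of 0.8; "Standard deviation: 0.52"; "Effect size: 0.21"; and "Attrition rate: 15% in online studies". The SD and the effect size are taken from an earlier trial of a peer-led online safer-sex intervention (reference 19). The result is "112 people per intervention arm".

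The section prints no formula. It does not say whether 0.21 is a raw or a standardised difference, or whether 112 is before or after attrition.

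Under Data Analysis the protocol plans a comparison of means among other analyses: "Independent t-tests will be carried out to evaluate the score change within group and also between groups". The SAP has no sample size section, so nothing there corrects or explains these inputs.

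**The concern.** β conventionally denotes the type II error. Printed as 0.8, it describes a trial with an 80% chance of missing the effect it is designed to find, and that does not fit the sample size two lines further on. A reader can recover the intended power only by working backwards from 112.

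Two smaller matters follow. The label on 0.21 does not state its scale, although the sample size depends on it. And the step from evaluable to enrolled participants appears to add 15% to the requirement, which is not the same as allowing for a 15% loss. At stake is the accuracy of the only sample size justification in the documents, and a small amount of power.

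**Working it through.** **Inputs** (Protocol, Sample size calculation): two-sided α = 0.05 (z = 1.95996), SD = 0.52, 0.21, attrition 15%, stated n = 112 per arm. **Assumed**: equal allocation (a single per-arm figure is given), individual randomisation, and an unadjusted comparison of two independent means.

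**Formula**: n per arm = 2 × (z for α + z for power)² × SD² / difference².

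**1. Reproducing 112.** With power 0.80 (z = 0.84162) and 0.21 as a raw difference (d = 0.21/0.52 = 0.404):

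- n = 2 × (1.95996 + 0.84162)² × 0.52² / 0.21² = 96.25, so 97 evaluable per arm. The t distribution gives 97.22, so 98.
- 97 × 1.15 = 111.55, rounded up to 112. This matches the protocol.

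**2. β taken literally as 0.8 (power 0.20, z = −0.84162).**

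- n = 2 × (1.95996 − 0.84162)² × 0.52² / 0.21² = 15.34, so 16 per arm.
- With attrition: 16 × 1.15 = 18.4 or 16 / 0.85 = 18.8; both round up to 19.

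**3. Other readings of the listed inputs.**

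| Reading | Before attrition | With attrition (× 1.15 to ÷ 0.85) |
|---|---|---|
| 0.21 standardised, power 0.80 | 356 | 410 to 419 |
| 0.21 standardised, power 0.20 | 57 | 66 to 68 |
| Raw 0.21, one-sided, power 0.80 | 76 | 88 to 90 |
| Raw 0.21, power 0.90 | 129 | 149 to 152 |

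None gives 112.

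**4. The attrition step.** To keep n evaluable after a 15% loss, enrolment must be n / 0.85:

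- 97 / 0.85 = 114.12, so 115; 98 / 0.85 = 115.29, so 116. That is 3 to 4 per arm more than 112.
- Conversely, 112 × 0.85 = 95.2, about 95 completers per arm, 2 to 3 below the 97 to 98 required.

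**5. Power with 95 completers per arm.**

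- Normal approximation: 0.21 / (0.52 × √(2/95)) = 2.783; 2.783 − 1.960 = 0.823; power = 79.5%.
- Noncentral t: 79.1%.
- Shortfall from 80%: 0.5 to 0.9 points.
- Difference detectable at 80% power: 2.80158 × 0.52 × √(2/95) = 0.211 (0.212 by t), against 0.21.

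**6. Break-even attrition.** 1 − 97/112 = 13.4%; 1 − 98/112 = 12.5%. At or below these rates 112 is enough.

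**The case against.** **It is a notation slip.** Since 112 arises only with power 0.80, the trial was sized for 80% power and the printed β changed nothing. That is right. A leading one-minus sign may even have been lost when the PDF was read, though this cannot be shown, so the sponsor should look at the source file. A reader might infer from the printed β that the trial has only 20% power; the protocol's own sample size rules that out. The text still needs correcting, because it stands in the only justification given.

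**The scale of 0.21.** A reader might infer from the words used to label it that 0.21 is standardised, that 356 per arm are needed, and that the trial is badly underpowered. The documents do not support this. An SD is listed directly above 0.21 and is not needed for a standardised effect, and the raw reading reproduces 112. What remains is a request to confirm the scale in the cited study, which the documents do not show, and to label it.

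**The 79% is not for the planned analysis.** The protocol specifies intention to treat, and the SAP adds last observation carried forward, a Mann-Whitney test and a linear model adjusted for baseline. Several parts of this stand:

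- Carrying values forward would keep all 112 in the analysis, with nominal power of 85.3% (t). But it supplies no observed one-month outcome for those lost and may dilute the effect, so it does not make good the attrition that the protocol itself budgets for.
- Baseline adjustment could close the gap. If the baseline to follow-up correlation were 0.15, 0.2 or 0.3 (assumed values), power with 95 per arm would be 80.0%, 80.7% or 82.7%.
- In the other direction, the Study design section allows cluster randomisation of Yijin students. If everyone were randomised in classes of 20 (an assumption), power would be about 72% at an intracluster correlation of 0.01 and 66% at 0.02. The documents give neither figure, and only part of the sample may be clustered.

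The 79% must therefore be stated with its conditions.

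**The shortfall is immaterial.** It is very small, and 15% is itself a planning assumption. This stands, and it is why no change in enrolment is proposed.

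**Conclusion.** The concern holds, and it is minor. The printed β is inconsistent with the stated 112 per arm. Of the readings tried, only power 0.80 with 0.21 as a raw mean difference leads to 112. That 15% was added by multiplication is inferred from the exact match, since no formula is printed; the shortfall does not depend on that inference, because 112 with 15% lost leaves about 95 completers however 112 was reached.

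The gap is 2 to 3 completers per arm and 0.5 to 0.9 points of power. This rests on equal allocation, individual randomisation, 15% attrition, a raw difference of 0.21 with SD 0.52, and an unadjusted comparison of means among completers. Clustering and baseline adjustment are outside this calculation.

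**What to change.** In the protocol's sample size section:

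- Replace the β entry with: power = 0.80 (β = 0.20).
- Check the scale of 0.21 in the cited study (reference 19). If it is confirmed as raw, label it: raw mean difference 0.21 (d = 0.40 with SD 0.52).
- Then add: 97 to 98 evaluable per arm are needed; 112 enrolled with 15% attrition leaves about 95 completers and about 79% power for an unadjusted comparison of means among completers, assuming individual randomisation, with no allowance for clustering or for baseline adjustment.

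If the check shows that 0.21 is a standardised effect, the calculation must be redone and the added sentence must not be used.

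The cost is a text correction and one look at a cited paper. Enrolment and conduct need not change if the raw reading is confirmed. The only downside is that the stated power becomes slightly less favourable, about 79% in place of 80%.

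### The protocol assigns an independent t-test to within-group change in paired scores, contradicting its own paired t-test, and neither document says which between-arm analysis is primary

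*Protocol*

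**What the plan says.** The same participants answer a baseline questionnaire, an immediate post-intervention questionnaire and a 1-month questionnaire, and 1 month is the primary endpoint (Protocol, Delivery of Intervention and Assessment of Efficacy).

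The protocol's Data Analysis section then gives, in order:
- For outcome evaluation, "paired t-tests will be used to examine within group outcome changes".
- For the primary outcome score, a linear regression comparing the two arms. No baseline covariate is named.
- In the next paragraph: "Independent t-tests will be carried out to evaluate the score change within group and also between groups".
- Finally: "The outcome difference at baseline and at follow-up will also be evaluated with linear regression". The model terms are not given.

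The SAP's Statistical Methods section contains no within-group test of change. Its only t-test compares scaled outcomes at baseline. Between arms at follow-up it uses Mann-Whitney U, citing skewed outcomes. It also lists a univariate linear regression and a multiple linear model that adjusts for the baseline value of the outcome. It does not rank these analyses.

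**The concern.** Two tests are assigned to one quantity, the change within an arm, and one of them does not fit the data. An independent t-test treats an arm's baseline and follow-up scores as two unrelated samples. It ignores their correlation, so its standard error and p-value are wrong. An analyst following the protocol literally could report one within-arm change as significant by the paired test and not significant by the independent test.

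The between-arm question is the one that the trial is randomised to answer, and several analyses compete for it. They differ in precision and in what they estimate: Mann-Whitney U gives no adjusted mean difference, and the change-score t-test makes weaker use of baseline than a model that adjusts for it. With no primary analysis named, the choice could be made after the results are seen.

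**Working it through.** **Inputs.** From the protocol's Sample size calculation: "α (two-tailed) of 0.05"; β printed as 0.8, read here as power 0.80; "Standard deviation: 0.52"; "Effect size: 0.21"; attrition 15%; "112 people per intervention arm". The baseline–follow-up correlation ρ is in neither document, so it is assumed at 0.3, 0.5 and 0.7. Equal variances and a normal approximation are used throughout.

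**1. The plan's own figure.** Reading 0.21 as a raw mean difference:

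n per arm = 2 × [0.52 × (1.960 + 0.842) / 0.21]² = 96.25, rounded up to 97.

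Multiplying by 1.15 gives 111.55, hence 112, which matches. (Dividing by 0.85 gives 114.1, hence 115.) The calculation compares two independent means and uses no baseline correlation. Evaluable per arm: 112 × 0.85 = 95.2, taken as 95.

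**2. Independent t-test applied to one arm's paired scores.** The true variance of the mean change is 2σ²(1 − ρ)/n. The independent test uses 2σ²/n.
- SE ratio = 1/√(1 − ρ)
- True two-sided type I error = 2[1 − Φ(1.96/√(1 − ρ))]
- For a within-arm change of 0.21 with n = 95, the uncorrelated SE is 0.52 × √(2/95) = 0.0754, and 0.21/0.0754 = 2.783. Power of the independent test = Φ[(2.783 − 1.96)/√(1 − ρ)]; power of the paired test = Φ[2.783/√(1 − ρ) − 1.96].

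| ρ | SE too large by | True type I error | Power, independent | Power, paired |
|---|---|---|---|---|
| 0.3 | 1.20 | 1.9% | 84% | 91% |
| 0.5 | 1.41 | 0.6% | 88% | 98% |
| 0.7 | 1.83 | 0.03% | 93% | >99% |

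**3. Between-arm analyses, if 0.52 is the SD of a single score.** Power = Φ[2.783/√v − 1.96], with v = 1 for follow-up only, v = 2(1 − ρ) for the change score and v = 1 − ρ² for the baseline-adjusted model.

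| ρ | Follow-up only | Change score | Baseline-adjusted |
|---|---|---|---|
| 0.3 | 79% | 65% | 83% |
| 0.5 | 79% | 79% | 90% |
| 0.7 | 79% | 95% | 97% |

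The variance ratio of change score to adjusted model is 2/(1 + ρ) = 1.54, 1.33 and 1.18. Below ρ = 0.5 the change score is also less powerful than ignoring baseline altogether.

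**4. Sample size for the adjusted model.** 96.25 × (1 − ρ²), rounded up, is 88, 73 and 50 per arm. Dividing by 0.85 gives 104, 86 and 59, all below 112.

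**5. If 0.52 is instead the SD of a change.** Change-score power is 79% at every ρ. The adjusted variance is (1 + ρ)/2 = 0.65, 0.75 and 0.85 of the change-score variance, so adjusted power is Φ[2.783/√0.65 − 1.96] = 93%, and likewise 90% and 86%. The size of the gain depends on the reading; the ordering does not.

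**The case against.** The strongest reply is that this is a drafting slip. The correct paired test is already named one paragraph earlier, and the SAP carries no within-group test at all. That limits the consequence, but the protocol sentence still stands and nothing in the SAP withdraws it.

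Several stronger readings are tempting, and the reply defeats them:
- *The plan has no baseline-adjusted between-arm estimate.* It has one: the SAP's multiple linear model adjusts for the baseline outcome, and the protocol plans a between-arm regression for the primary outcome. What is missing is a statement that the adjusted model is primary.
- *The t-test on change between groups is invalid.* Under randomisation it is valid, only less precise.
- *The wrong test inflates false positives.* With positive correlation it does the reverse.
- *An ineffective website could be declared effective because one arm's p-value crosses 0.05.* No text says that effectiveness will be judged by comparing within-arm p-values, and the sentence directly after the paired t-tests sets out a between-arm comparison. The within-arm tests do appear under outcome evaluation without a descriptive label, so adding one is sensible; it closes a gap and does not correct a stated rule.
- *The two within-arm tests can give opposite answers.* Both use the same mean change, so the direction agrees. Only significance can differ.

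Two further cautions stand. The protocol does not say whether 0.52 is the SD of a score or of a change, so the power figures are conditional on that. The sentence "The outcome difference at baseline and at follow-up will also be evaluated with linear regression" may mean a regression of change or a between-arm comparison at each time point, so it cannot be counted with certainty as a change-score analysis.

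**Conclusion.** The point holds in two parts.

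First, the protocol names the wrong test for within-group change and contradicts itself. At assumed correlations of 0.3 to 0.7 the standard error is inflated 1.20 to 1.83 times, and the nominal 5% test runs at about 1.9% down to 0.03%. The error is conservative: its cost is missed change and a p-value at odds with the paired test, not false claims of benefit.

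Second, neither document designates a primary between-arm analysis, although the SAP already contains the most suitable one. If 0.52 is the SD of a single score, that model has 83% to 97% power with 95 evaluable per arm, against 65% to 95% for the change score.

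A reader might infer that the sample size is undermined. It is not: 112 reproduces, and it suffices for the adjusted model at these correlations.

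The figures assume equal variances and independent participants. Possible cluster randomisation of the Yijin students and the SAP's carrying forward of last observations are not modelled.

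**What to change.** - **Protocol, Data Analysis:** delete the within-group use from the independent t-test sentence. Keep the paired t-tests, state that they are descriptive, and state that no claim of effectiveness rests on them. Clarify what the final regression sentence models.
- **Both documents:** name one primary between-arm analysis, the SAP's baseline-adjusted linear model: 1-month score regressed on arm and baseline score, reporting the adjusted mean difference with its 95% CI.
- **Both documents:** list the change-score t-test, the unadjusted regression and Mann-Whitney U as supportive or sensitivity analyses. Mann-Whitney U keeps a purpose there because the SAP reports skewed outcomes.
- **Protocol, Sample size calculation:** say whether 0.52 is the SD of a score or of a change.

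The cost is wording. No new data are needed, because baseline scores are already collected. No larger sample is needed at the correlations considered if 0.52 is the SD of a single score.

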Evaluation of a	ı peer-led we	b-based int	tervention f	or safe usa	ige of d	ating
applica	tions in Hong	g Kong: a r	andomized	controlled	trial	

Statistical Analysis Plan

August 2018

(Version 1. Dated 17.08.2018)

Principle Investigator: [name]
Address: Department of Family Medicine and Primary Care, [name]
Co-Investigators: [name], [name]

Statistical Methods

The demographics were described and differences in baseline were assessed using chi-square tests for categorical variables for e.g. age, gender and sexual orientation; and, *t*-test for scaled outcomes. The satisfaction of the intervention at post-intervention was analysed using chi-square test. ITT with the "last observation carried forward" values was adopted. Due to the skewness distribution of the outcomes, the differences of intervention at follow-ups were assessed using Mann-Whitney U-test. Univariate linear regression and multiple linear model was used to evaluate the significant factors between the intervention and control groups and after the adjustment of baseline outcome measurements respectively. All data were entered, cleaned and analysed using SPSS (Version 25) and significant tests were set at P-values <0.05.

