Due to the aforementioned reasons, we believe that that a web based peer-led intervention to educate the public on dating application risks would be effective and appropriate. In this study, we evaluate the effectiveness of a web-based peer-led intervention to promote safe usage of dating applications among young adults aged 18-27 in Hong Kong. The trial will be conducted in compliance with the protocol, GCP, and the applicable regulatory requirements.

Trial Objectives and Purpose

Aim: To promote safe usage of dating applications among young adults in Hong Kong

Objectives

- To evaluate the effectiveness of a web-based, peer-led intervention in:
 - Providing appropriate and reliable information about dating applications to young adults in Hong Kong
 - Increasing the awareness of dating application associated risks and benefits among young adults in Hong Kong
 - Improving the attitudes towards risk perception and the safe usage of dating applications among young adults in Hong Kong

• Promoting behavioral skills related to the safe usage of dating applications in young adults in Hong Kong, specifically in preventing and handling negative experiences associated with dating applications

Trial Design

Study design

The study will use an open-labeled randomized control trial design with one intervention arm and one control. The control will have access to an online resource with similar interactive elements and time usage on a different topic. Both arms will complete the baseline and final questionnaire. There will not be any blinding as it is an open labeled study but participants will be randomly assigned to the intervention or control arm with a randomization software. Students in the Yijin program may be randomized by clusters to minimize the chance of contamination.

Intervention

The intervention is a web-based resource including text content, 4 videos, a scenario game and a risk assessment. The program can be accessed on both phones and other mobile devices such as smart phones and ipads. The topics of each segment is listed below:

Video 1: Introduction of the theme that meeting people on dating apps and meeting friends in real life present the same risks. The focus is that users should not have assumptions when meeting people in either context. This video also touches upon social expectations and pressures to pay for dates, leading to potential risk of falling victim to monetary scams.

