The primary endpoint will be 1 month after the delivery of the intervention. Students will fill out a baseline questionnaire before the delivery of the intervention and an immediate post questionnaire. 1 month later, students will access a follow-up questionnaire via HKU Survey Gizmo, a secure survey tool to ensure all data is kept confidential. The details of the delivery method of the follow-questionnaire will be discussed with the college's staff. Research staff may attend a special session or class to delivery the follow-up questionnaire. Another option is to have teachers deliver the follow up questionnaire. The follow-up questionnaire will be online hence participants will be able to access it on their computers, phones, or other mobile devices. Participants are estimated to participant in the trial for no longer than 4 months. Participants are allowed to withdraw from the study at any point in time without any criterion.

Selection and Withdrawal of Subjects

Inclusion criteria

- Aged 17-27
- Able to read and understand Chinese
- Able to provide an active email

Exclusion criteria

- People who have a physical impediment in which they cannot access the material in the intervention

Participants are allowed to withdraw from the study at any point in time without any criterion. We will utilize the "intention to treat" approach to deal with subjects withdrawn.

Treatment of Subjects

The intervention is a web based intervention and will not involve any medical treatments, drugs, or pharmaceuticals. The route of administration is access through any device that can access web-based content and the dosage is one visit.

Assessment of Efficacy

Evaluation will be done with an online survey tool called HKU Survey Gizmo. There will be a pre questionnaire containing baseline demographics and other questions concerning dating application usage. The participants will be given 30-45 minutes to access the program. Following that, the participants will be given a post questionnaire. 1 month later, the participants will be asked to fill in a follow up questionnaire.

Assessment of Safety

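### Last observation carried forward is the only missing-data rule, so at 15% attrition about 17 of 112 per arm would enter the 1-month analysis with a baseline or immediate-post score

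*SAP*

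**What the plan says.** On timing, the Protocol (Delivery of Intervention) states: "The primary endpoint will be 1 month after the delivery of the intervention". The same section lists a baseline questionnaire, an immediate post questionnaire and a 1-month follow-up. Assessment of Efficacy allows 30-45 minutes of access and continues: "Following that, the participants will be given a post questionnaire".

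On losses, the sample size section assumes 15% attrition, taken from other online studies, and gives 112 people per arm. For withdrawals the Protocol (Selection and Withdrawal of Subjects) says only: "We will utilize the 'intention to treat' approach to deal with subjects withdrawn". That settles who is analysed, not what value stands in for a missing score.

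The SAP (Statistical Methods) supplies the value: "ITT with the 'last observation carried forward' values was adopted". No other missing-data method appears in either document.

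On analysis, the Protocol says: "For the primary outcome that is a score, linear regression will be used to evaluate the difference between the control and intervention group". The SAP adds a multiple linear model adjusted for the baseline outcome, and also: "Due to the skewness distribution of the outcomes, the differences of intervention at follow-ups were assessed using Mann-Whitney U-test".

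**The concern.** The endpoint asks whether the intervention has an effect one month later. For a participant missing at that visit, carry-forward answers with a score taken either minutes after exposure or before it. The first overstates a fading effect. The second counts the participant as unchanged and dilutes a real effect.

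The rule is unbiased only under particular conditions. One sufficient set is that the post score is the one carried, that the arm difference is stable from post to 1 month, and that dropout is random and equal across arms. The SAP states none of these and plans nothing that would show whether the conclusion depends on them. At stake is a modest bias in the primary estimate, whose direction a reader could not judge from the plan.

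**Working it through.** **Inputs from the Protocol.** Two-sided alpha 0.05; SD 0.52; effect 0.21; attrition 15%; 112 per arm. I read 0.21 as a raw mean difference and the printed beta of 0.8 as power, because that reading reproduces the stated size.

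**The plan's own figure.** n = 2 × [0.52 × (1.960 + 0.842) / 0.21]² = 96.3, so 97 per arm. 97 × 1.15 = 111.6, so 112, as stated.

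**Number affected.** 112 × 0.15 = 16.8, about 17 per arm. That leaves 112 × 0.85 = 95.2 observed.

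**Bias formula.** With a the share carried, d1 the true 1-month difference and d0 the arm difference in the carried score, and with random, equal dropout:

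expected estimate = (1 − a) × d1 + a × d0.

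The unadjusted standard error is 0.52 × √(2/112) = 0.0695 with everyone included, and 0.52 × √(2/95.2) = 0.0754 on observed scores.

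The post effects, correlations and dropout patterns below are assumptions. Simulated results use individual randomisation and, except where noted, normal scores.

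**Post score carried, effect fades.**
- Full fading (d0 = 0.21, d1 = 0): 0.15 × 0.21 = 0.0315, or 6% of an SD, instead of 0. The unadjusted normal approximation rejects 7.4% of the time. By simulation, Mann-Whitney rejects about 7%. The baseline-adjusted model rejects about 7-8%, 8-9% and 11-12% at correlations 0.3, 0.6 and 0.8. On observed scores both stay at 4.9-5.2%.
- Half fading (d1 = 0.105): 0.85 × 0.105 + 0.15 × 0.21 = 0.121. Coverage is 94-95%.
- Smaller effect, full fading (d0 = 0.105, d1 = 0): 0.15 × 0.105 = 0.016. Rejection is 5.6-5.8%.
- Full fading with one skewed shape (lognormal, sigma 0.8, correlation 0.6): the adjusted carry-forward model rejects 8.0%.

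**Baseline carried, true effect 0.21** (d0 = 0).
- Estimate: 0.85 × 0.21 = 0.1785.
- Unadjusted power: 72.9%, against 79.6% on observed scores, a loss of about 7 points.
- Baseline-adjusted model at correlation 0.3: 78.6% against 82.0%. Over the correlations examined the loss is about 1-3 points.
- Coverage of the adjusted carry-forward model at correlation 0.3: about 91-92%.

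**Post score carried, constant effect of 0.21.**
- Random, equal dropout: 0.85 × 0.21 + 0.15 × 0.21 = 0.21, so no bias. Power at correlation 0.3 is about 88%, against about 83% on observed scores.
- Dropout related to the post score in the same way in both arms: 0.21-0.22, coverage 95%.
- Dropout related to the post score in the intervention arm only (odds tripled per SD lower), correlation 0.3: carry-forward gives 0.165, power 68%, coverage 89.7%. Observed scores give 0.224, coverage 94.5%. Multiple imputation by arm using the post score gives 0.209-0.212, coverage about 95%.

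**The case against.** The best defence is that carry-forward keeps all randomised participants in the analysis, as the Protocol's intention-to-treat statement wants, and that any harm is small. Under a constant effect and random, equal dropout with the post score carried, it is unbiased and has about 5 points more power than the observed-score model. Half fading barely touches coverage. The 11-12% false-positive rate needs both complete loss of a 0.21 effect in a month and a correlation of 0.8. If baseline is carried, the error is conservative. Most of the simulations use normal scores although the SAP calls the outcomes skewed. All of this stands and limits the size of the point. It does not remove it: keeping everyone in the analysis set does not turn an earlier score into a 1-month score.

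Some stronger readings also need to be set aside.
- *That the immediate-post score is what would be carried.* The Protocol schedules a post questionnaire, and the SAP speaks of follow-ups in the plural. But Study design mentions only a baseline and a final questionnaire, and the only analysis the SAP expressly ties to post-intervention is satisfaction. Neither document says that the post questionnaire scores the primary outcome.
- *That the rule favours the intervention.* This needs a carried post score and a fading effect. With baseline carried, a real effect is diluted.
- *That the planned model loses 7 points of power.* That figure is for the unadjusted comparison.
- *That dropout will seriously distort the result.* The scenario with 68% power needs selective dropout in one arm and random dropout in the other. Nothing in the documents suggests that pattern.
- *That 17 per arm is a forecast.* The 15% comes from other studies and is not tied to a visit or arm. In-class delivery of the follow-up questionnaire could change it.
- *That the standard errors are wrong.* At correlation 0.3 the adjusted carry-forward model's mean standard error was 0.0667, against an empirical 0.0661.

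**Conclusion.** The point holds as a moderate one that should be fixed. The SAP's sole missing-data rule substitutes an unspecified earlier score for the 1-month outcome, in about 17 of 112 per arm at the planning rate, with no stated assumption and no check. The estimate could be about 0.03 too high if a post effect of 0.21 is carried and has vanished, or about 0.03 too low (0.18 for 0.21) if baseline is carried. It could also be unbiased. Larger error needs dropout that differs by arm.

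These sizes rest on SD 0.52, 15% missing in each arm, individual randomisation and the assumed effects and correlations. Confidence is high on what the documents say and medium on the size. The case for change is that the plan already contains a model that avoids relying on these conditions, at little cost.

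**What to change.** In the SAP, Statistical Methods:

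1. Make the main 1-month analysis the baseline-adjusted linear model already planned, fitted to observed 1-month scores, and state the missing-at-random assumption.
2. If the post questionnaire does score the primary outcome, multiple imputation by arm using baseline and the post score may be used instead. It also covers dropout that depends on the post score. Predictive mean matching suits skewed scores.
3. State which score carry-forward uses, and keep it only as a secondary run.
4. Report missing 1-month scores by arm.
5. Add one delta-shift analysis: move the values assumed for missing intervention-arm participants against the intervention, in steps such as 0.1 of the trial's own baseline SD, until the conclusion changes. At 15% missing, each step moves the estimate by 0.15 × 0.1 = 0.015 SD.

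The cost is SAP wording and a little analysis time, with no new visits or data. The observed-score model needs no extra software; imputation assumes that the SPSS installation includes it. There are two downsides. The analysis relies on missing at random, which step 5 probes. It also gives up about 5 points of power where carry-forward happens to be unbiased.
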